a. State how the PI, or named designee, ensures that an investigational device is used only in accordance with the research protocol approved by the HIC, and maintains control of the investigational device as follows:

Maintains appropriate records, including receipt of shipment, inventory at the site, dispensation or use by each participant, and final disposition and/or the return of the investigational device (or other disposal if applicable):

Documents pertinent information assigned to the investigational device (e.g., date, quantity, batch or serial number, expiration date if applicable, and unique code number):

Stores the investigational device according to the manufacturer's recommendations with respect to temperature, humidity, lighting, and other environmental considerations:

Ensures that the device is stored in a secure area with limited access in accordance with applicable regulatory requirements:

Distributes the investigational device to subjects enrolled in the IRB-approved protocol:

SECTION VII: RECRUITMENT/CONSENT AND ASSENT PROCEDURES

1.

Targeted Enrollment: Give the number of subjects:

a. targeted for enrollment at Yale for this protocol 60
 b. If this is a multi-site study, give the total number of subjects targeted across all sites

2.

Indicate recruitment methods below. Attach copies of any recruitment materials that will

be used.

 Flyers	 Internet/Web Postings	 Radio
 Posters	 Mass E-mail Solicitation	 Telephone
 Letter	 Departmental/Center Website	 Television
 Medical Record Review	 Departmental/Center Research Boards	 Newspaper
 Departmental/Center Newsletters	 Web-Based Clinical Trial Registries	
 YCCI Recruitment database	 Clinicaltrials.gov Registry (do not send materials to HIC)	
 Other (describe): Yale Diabetes Registry (HIC# 0911005973)		

3.

Recruitment Procedures:

a. Describe how potential subjects will be identified.

Subjects will be recruited by flyers that will be posted locally. The flyer will display the contact information of the study team. They may also be identified at the Adult Endocrine Clinic and Yale University Health Services and approached through their caregiver. In addition the diabetes registry will be used to identify eligible patients and contact them by phone or letter, since this category of patients have already given their consent to be contacted for potential trials. Furthermore, they will be recruited through YCCI website, ClinicalTrials.gov website and community clinics. They will then be offered to contact one of the research team members or if they give their approval, to be contacted by the team by phone or e-mail and they will provide the subject with additional information about the study and the investigator will determine the eligibility of the subject for the study. The purpose and potential complications of the study will be explained to each subject in detail.

During the screening session, the informed consent form and study details are reviewed in detail by one of the project investigators and the subject will be asked to read the informed consent form (approved by the Yale Human Investigations committee). The subject will be given time to ask questions and only after that will the subject be asked to give informed consent to participate. The informed consent form and study details will again be reviewed with the subject on each study day prior to beginning the study.

b. Describe how potential subjects are contacted.

The consent process is a two-step process, whereby the subject initiates contact via telephone or in person presentation and will undergo a phone or in person screen with a member of the research team. Thereafter, potentially eligible candidates will be scheduled for a face-to-face interview.

c. Who is recruiting potential subjects? See IRES IRB

4.

Screening Procedures

- a. Will email or telephone correspondence be used to screen potential subjects for eligibility prior to the potential subject coming to the research office? Yes No
- b. If yes, identify below all health information to be collected as part of screening and check off any of the following HIPAA identifiers to be collected and retained by the research team during this screening process.

HEALTH INFORMATION TO BE COLLECTED:

HIPAA identifiers:

- Names
- All geographic subdivisions smaller than a State, including: street address, city, county, precinct, zip codes and their equivalent geocodes, except for the initial three digits of a zip code if, according to the current publicly-available data from the Bureau of the Census: (1) the geographic unit formed by combining all zip codes with the same three initial digits contains more than 20,000 people, and (2) the initial three digits of a zip code for all such geographic units containing 20,000 or fewer people is changed to 000.
- Telephone numbers
- Fax numbers
- E-mail addresses
- Social Security numbers
- Medical record numbers
- Health plan beneficiary numbers
- Account numbers
- All elements of dates (except year) for dates related to an individual, including: birth date, admission date, discharge date, date of death, all ages over 89 and all elements of dates (including year) indicative of such age, except that such ages and elements may be aggregated into a single category of age 90 or older
- Certificate/license numbers
- Vehicle identifiers and serial numbers, including license plate numbers
- Device identifiers and serial numbers
- Web Universal Resource Locators (URLs)
- Internet Protocol (IP) address numbers
- Biometric identifiers, including finger and voice prints
- Full face photographic images and any comparable images
- Any other unique identifying numbers, characteristics, or codes

5.

Assessment of Current Health Provider Relationship for HIPAA Consideration:

Does the Investigator or any member of the research team have a direct existing clinical relationship with any potential subject?

- Yes, all subjects
- Yes, some of the subjects
- No

If yes, describe the nature of this relationship.

An investigator may be the treating clinician for subjects recruited from the Endocrine Clinic.

6.

Request for waiver of HIPAA authorization: (When requesting a waiver of HIPAA

Authorization for either the entire study, or for recruitment purposes only. Note: if you are collecting PHI as part of a phone or email screen, you must request a HIPAA waiver for recruitment purposes.)

Choose one: For entire study: _____ For recruitment purposes only: X

- i. Describe why it would be impracticable to obtain the subject's authorization for use/disclosure of this data;
We will need the volunteers' full name, address, date of birth, and phone numbers to schedule a screening visit at the Hospital Research Unit. We also would like to be able to review clinic appointments to see if any of the scheduled patients meet the inclusion criteria prior to calling them on the phone. This would include reviewing their diagnosis for DM, their age to be between 18-65 years, and their Body Mass Index (BMI). By reviewing this information prior to contact, we will be able to avoid contacting subjects that may not be included due to BMI and age.
- ii. If requesting a waiver of **signed** authorization, describe why it would be impracticable to obtain the subject's signed authorization for use/disclosure of this data;

By signing this protocol application, the investigator assures that the protected health information for which a Waiver of Authorization has been requested will not be reused or disclosed to any person or entity other than those listed in this application, except as required by law, for authorized oversight of this research study, or as specifically approved for use in another study by an IRB.

Researchers are reminded that unauthorized disclosures of PHI to individuals outside of the Yale HIPAA-Covered entity must be accounted for in the "accounting for disclosures log", by subject name, purpose, date, recipients, and a description of information provided. Logs are to be forwarded to the Deputy HIPAA Privacy Officer.

7. Required HIPAA Authorization: If the research involves the creation, use or disclosure of protected health information (PHI), separate subject authorization is required under the HIPAA Privacy Rule. Indicate which of the following forms are being provided:

- Compound Consent and Authorization form

HIPAA Research Authorization Form

8. Process of Consent/Accent: Describe the setting and conditions under which consent/assent will be obtained, including parental permission or surrogate permission and the steps taken to ensure subjects' independent decision-making.

The study will be described to the subject in detail, including the purpose and potential risks associated with the study. This will be explained by the physician, including the intervention and process for the study day. The subject will be required to read and sign the consent form approved by the HIC, and the patient will retain a copy of this consent to review. Additionally, the patient will have sufficient time to ask questions during the screening and will be encouraged to contact investigators with further questions or concerns. All subjects who will be asked to volunteer are informed that no immediate personal medical benefits will be derived from participation. Any subject who appears incapable of providing informed consent (e.g., due to apparent cognitive impairment) will be excluded. Subjects will be informed that they can decline to participate in the study without penalty, and given the opportunity to withdraw from the study prior to analysis of their data. All subjects will be given a copy of the consent form enclosed with this protocol outlining the risks and benefits of participation in this study. Following the resolution of any questions, the subjects will be asked to sign the consent form, if he/she agrees to participate.

9. Evaluation of Subject(s) Capacity to Provide Informed Consent/Accent: Indicate how the personnel obtaining consent will assess the potential subject's ability and capacity to consent to the research being proposed.

We do not plan to recruit subjects with limited decision-making capacity. Potential subjects will undergo a face-to-face interview. At that time, a study physician will meet the subject, review the informed consent form, explain the purpose of the study and risks associated with participation, and will be available for questions. To ensure that the study subject understands the study, the subject will be asked questions about the study procedures and the risks associated with participation. If any concern arises that the study subject did not fully understand the study, the study physician may decide that the subject is not suitable for participation. If the subject is still interested after all questions have been answered, a study physician will ask the subject to sign the informed consent form.

10. Documentation of Consent/Accent: Specify the documents that will be used during the consent/assent process. Copies of all documents should be appended to the protocol, in the same format that they will be given to subjects.

There will be a specific Compound Consent and Authorization form.

11. Non-English Speaking Subjects: Explain provisions in place to ensure comprehension for research involving non-English speaking subjects. Translated copies of all consent materials must be submitted for approval prior to use.

N/A, we do not plan to recruit non-English speaking subjects.

12. Consent Waiver: In certain circumstances, the HIC may grant a waiver of signed consent, or a full waiver of consent, depending on the study. If you will request either a waiver of consent, or a waiver of signed consent for this study, complete the appropriate section below.

- Not Requesting a consent waiver**
- Requesting a waiver of signed consent**
- Requesting a full waiver of consent**

A. Waiver of signed consent: (Verbal consent from subjects will be obtained. **If PHI is collected, information in this section must match Section VII, Question 6**)

- Requesting a waiver of signed consent for Recruitment/Screening only**

If requesting a waiver of signed consent, please address the following:

- a. Would the signed consent form be the only record linking the subject and the research?
 Yes No
- b. Does a breach of confidentiality constitute the principal risk to subjects?
 Yes No

OR

- c. Does the research activity pose greater than minimal risk?

Yes **If you answered yes, stop. A waiver cannot be granted.** Please note:

Recruitment/screening is generally a minimal risk research activity

- No

AND

- d. Does the research include any activities that would require signed consent in a non-research context? Yes No

- Requesting a waiver of signed consent for the Entire Study** (Note that an information sheet may be required.)

If requesting a waiver of signed consent, please address the following:

- a. Would the signed consent form be the only record linking the subject and the research?
 Yes No
- b. Does a breach of confidentiality constitute the principal risk to subjects?
 Yes No

OR

- c. Does the research pose greater than minimal risk? Yes **If you answered yes, stop. A waiver cannot be granted.** No

AND

- d. Does the research include any activities that would require signed consent in a non-research context? Yes No

B. Full waiver of consent: (No consent from subjects will be obtained for the activity.)

- Requesting a waiver of consent for Recruitment/Screening only**

- a. Does the research activity pose greater than minimal risk to subjects?

Yes ***If you answered yes, stop. A waiver cannot be granted.*** Please note:
Recruitment/screening is generally a minimal risk research activity
 No
b. Will the waiver adversely affect subjects' rights and welfare? Yes No
c. Why would the research be impracticable to conduct without the waiver?
d. Where appropriate, how will pertinent information be returned to, or shared with subjects at a later date?

Requesting a full waiver of consent for the Entire Study (Note: If PHI is collected, information here must match Section VII, question 6.)

If requesting a full waiver of consent, please address the following:

a. Does the research pose greater than minimal risk to subjects?
 Yes ***If you answered yes, stop. A waiver cannot be granted.***
 No
b. Will the waiver adversely affect subjects' rights and welfare? Yes No
c. Why would the research be impracticable to conduct without the waiver?
d. Where appropriate, how will pertinent information be returned to, or shared with subjects at a later date?

SECTION VIII: PROTECTION OF RESEARCH SUBJECTS

Confidentiality & Security of Data:

a. What protected health information (medical information along with the HIPAA identifiers) about subjects will be collected and used for the research?

- Name
- Address
- Phone number
- Age
- Medical record number
- Race
- Past medical, and surgical history, allergies, medications taken.
- Family and social history
- Body mass index, vital signs
- Labs, including A1c, ALT/AST, creatinine, TSH, pregnancy test, and CGMS results

b. How will the research data be collected, recorded and stored?

Research data will be collected directly from the subject as well as via the electronic medical record. Subjects will be assigned a study number. The principal investigator will create a computer worksheet where the name of the subject's medical information is linked to the coded information. This will be housed on a password protected computer on a secured network. Only the investigators will have access to the computer records, which include the subject's identity, in order to evaluate the information generated by the study. No further

public disclosure of this information will be made. One copy of the consent form will be kept in a secured and locked cabinet in the PI's office (which is also locked). The subject's name will be kept separate from the results.

- c. How will the digital data be stored? CD DVD Flash Drive Portable Hard Drive Secured Server Laptop Computer Desktop Computer Other
- d. What methods and procedures will be used to safeguard the confidentiality and security of the identifiable study data and the storage media indicated above during and after the subject's participation in the study?

Do all portable devices contain encryption software? Yes No

If no, see <http://hipaa.yale.edu/guidance/policy.html>

All identifiable subject information that is collected during recruitment, screening, and participation will appear only on the initial paper forms, which will be kept under lock and key in the academic office of one of the study investigators. All digital files that could link a code number to an individual study subject will be password protected and stored on CD, which will be kept locked in the PI's office.

- e. What will be done with the data when the research is completed? Are there plans to destroy the identifiable data? If yes, describe how, by whom and when identifiers will be destroyed. If no, describe how the data and/or identifiers will be secured.

Procedures to ensure confidentiality follow the regulations and policies of the Yale University School of Medicine. The security mechanisms specified above in section **d** will continue to be in place to protect study data.

- f. Who will have access to the protected health information (such as the research sponsor, the investigator, the research staff, all research monitors, FDA, Yale Cancer Center Data and Safety Monitoring Committee (DSMC), SSC, etc.)? (please distinguish between PHI and de-identified data)

The NIDDK will be the only external agency that will have access to de-identified study data. Only the investigators will have access to PHI and de-identified data. The Yale University HIC will have access to study files.

- g. If appropriate, has a [Certificate of Confidentiality](#) been obtained? N/A
- h. Are any of the study procedures likely to yield information subject to mandatory reporting requirements? (e.g. HIV testing – reporting of communicable diseases; parent interview - incidents of child abuse, elderly abuse, etc.). Please verify to whom such instances will need to be reported. N/A

SECTION IX: POTENTIAL BENEFITS

Potential Benefits: Identify any benefits that may be reasonably expected to result from the research, either to the subject(s) or to society at large. (Payment of subjects is not considered a benefit in this context of the risk benefit assessment.)

Healthy non-diabetic subjects will have no direct benefit from the studies. Diabetic subjects will benefit by learning about their blood glucose levels while using the CGM.

SECTION X: RESEARCH ALTERNATIVES AND ECONOMIC CONSIDERATIONS

1. **Alternatives:** What other alternatives are available to the study subjects outside of the research? The alternative is to decline participation in the study.
2. **Payments for Participation (Economic Considerations):** Describe any payments that will be made to subjects, the amount and schedule of payments, and the conditions for receiving this compensation.
Participants will be paid \$150 for using the CGM, upon completion of the study. Compensation may be provided in the form of check or through Bank of America card issued through YCCI. In addition parking will be complementary.
3. **Costs for Participation (Economic Considerations):** Clearly describe the subject's costs associated with participation in the research, and the interventions or procedures of the study that will be provided at no cost to subjects.
There will be no additional cost to the study participants.
4. **In Case of Injury:** This section is required for any research involving more than minimal risk.
 - a. Will medical treatment be available if research-related injury occurs?
 - b. Where and from whom may treatment be obtained?
 - c. Are there any limits to the treatment being provided?
 - d. Who will pay for this treatment?
 - e. How will the medical treatment be accessed by subjects?

References

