- I have read a copy of the protocol and approve it being conducted at YNHH.
- I agree to notify the IRB if I am aware of any real or apparent institutional conflict of interest.
- The principal investigator of this study is qualified to serve as P.I. and has the support of the hospital for this research project.

YNHH HSPA Name (PRINT) and Signature

Date

For HIC Use Only

Date Approved

Human Investigation Committee Signature

This protocol is valid through _____

SECTION V: RESEARCH PLAN

1. Statement of Purpose: State the scientific aim(s) of the study, or the hypotheses to be tested.

To investigate whether the daily glucose profiles as assessed by continuous glucose monitoring for 1 week of normal weight, obese, and diabetic individuals relate to hunger levels and food intake.

2. Background: Describe the background information that led to the plan for this project. Provide references to support the expectation of obtaining useful scientific data.

The rising incidence of type 2 diabetes (T2DM) and obesity has paralleled the increased consumption of sugar, which has been associated with numerous adverse metabolic effects including weight gain, insulin resistance, cognitive decline, and stroke ¹⁻³.

Human studies using nuclear magnetic resonance spectroscopy (MRS), a powerful, non-invasive tool to determine the concentration of metabolites in living tissue, have shown that glucose transport across the BBB is not rate limiting during hyperglycemia ^{4,5}. Furthermore, in previous

work from our lab, brain glucose levels remain elevated in chronically hyperglycemic diabetic rats suggesting that there is very limited protective adaptation by the BBB⁶. We have also shown using microdialysis probes and hyperglycemic clamp in human subjects undergoing electrophysiological evaluation for epilepsy that brain microdialysate from non-epileptogenic brain areas showed a 200% rise in glucose levels from baseline during a hyperglycemic clamp⁷.

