Glucose has traditionally been considered a satiety signal in the brain. More than 50 years ago, Jean Mayer proposed the glucostatic theory of feeding where elevated glucose levels act as a satiety signal in the brain while falling glucose levels exert the opposite effect to stimulate hunger and subsequent food consumption⁸⁻¹². While our knowledge of the signals from the periphery to the brain that regulate eating behavior has expanded exponentially, much remains unknown about the mechanisms by which glucose regulates feeding behavior and how these pathways are altered in diabetes and obesity.

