Furthermore, previous published data from our lab¹³, subjects using a 2-step clamp, i.e. euglycemia (~90 mg/dL) followed by mild hypoglycemia (~65 mg/dL) in conjunction with fMRI and visual stimuli of food/non-food, showed that euglycemia was associated with activation of prefrontal cortex (PFC) and anterior cingulate ($p < 0.05$), while during hypoglycemia there was activation of hypothalamus, nucleus accumbens, insula, caudate and putamen in response to visual food cues ($p < 0.05$). In addition, hunger was increased during hypoglycemia as compared to the euglycemic phase (5.7 ± 0.5 vs 4.5 ± 0.5 ; $p < 0.01$). The study also included a small group of obese subjects ($n=5$). When this group was compared to lean subjects, they failed to show activation of the medial pre-frontal cortex during euglycemia and showed greater bilateral activation of the hypothalamus, striatum and insula in response to high-calorie food images during mild hypoglycemia ($p < 0.05$). Taken together the data suggest that during euglycemic phase of the clamp study there was activation of PFC in lean individuals, a region involved in complex cognitive behaviors, decision making and moderating correct social behavior¹⁴, whereas during hypoglycemic phase limbic regions were activated; which are involved in physiological and emotional responses¹⁵. Of particular interest these preliminary data suggest that the neural response to food consumption and food cues is altered in obese individuals in a way that could contribute to overeating behavior, namely increased stimulation of reward centers in response to nutrients (glucose) and/or food cues. This differentiated brain response could be a contributing factor to the pathogenesis of human obesity. We also plan to study patients with diabetes, who have chronic high glucose levels. Preliminary work from our group showed that obese unlike lean subjects suppressed activity in the ventral medial PFC (executive-control area) in response to food images; with a preferential liking/wanting for high-calorie food during hyperglycemia¹⁶. Therefore, we want to investigate if changes in circulating glucose levels can interfere with eating behavior and food intake in lean, obese subjects and patients with diabetes.

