Continuous glucose monitoring (CGM) is used in people with diabetes for better glycemic control as well as in non-diabetic individuals to characterize glucose patterns¹⁷⁻¹⁹. No study thus far has looked into glucose profiles normal weight, obese, and diabetic individuals in a normal, outpatient setting in relation to hunger and food intake. In a preliminary study of 8 individuals who wore a CGMS for 1 week and recorded their food intake and hunger levels, we found that increasing subjective hunger levels are more related to pre-prandial glucose peaks as opposed to nadirs. Furthermore, declines in glucose are correlated with caloric intake as well as the

macronutrient content of subsequent meals. Our findings suggest that glycemic excursions following a meal may play a role in hunger and food choices for the subsequent meal.

3. Research Plan: Summarize the study design and research procedures using non-technical language that can be readily understood by someone outside the discipline. Be sure to distinguish between standard of care vs. research procedures when applicable, and include any flowcharts of visits specifying their individual times and lengths. Describe the setting in which the research will take place.

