This is a pilot project. We estimate that a sample size of 15 subjects per group will provide 80% power to detect within group differences of 1.1 standard deviations. For changes in hunger ratings of liking, wanting and hunger we will have at least 80% power to detect between group differences across all glycemic conditions (i.e. main effect of group) of 1.0 standard deviation and within each condition of 1.25 standard deviations.

SECTION VI: RESEARCH INVOLVING DRUGS, BIOLOGICS, RADIOTRACERS, PLACEBOS AND DEVICES

N/A

A. DRUGS, BIOLOGICS and RADIOTRACERS

1. **Identification of Drug, Biologic or Radiotracer:** What is (are) the **name(s)** of the drug(s) biologic(s) or radiotracer(s) being used? Identify whether FDA approval has been granted and for what indication(s).

All protocols which utilize a drug, biologic or radiotracer **not** approved by, but regulated by, the FDA, or a radiotracer regulated by the RDRC, must provide the following information:

- a. What is the Investigational New Drug (IND) **number** assigned by the FDA?
- b. Who holds the IND?
- c. All protocols which utilize a radiotracer not approved by, but regulated by the FDA must provide the IND number: _____
Alternatively, use of the investigational radiotracer may be under RDRC/RSC oversight: (check if appropriate) _____

For all investigational radiotracers, attach a copy of the RDRC/RSC application (for radioisotopes used in the PET Center, PET Center personnel may complete this step)
Go to <http://rsc.med.yale.edu/login.asp?url=myApps.asp>. When you have logged in, complete the application and attach a copy to this submission.

Alternatively, an **exemption from IND filing requirements** may be sought for a clinical investigation of a drug product that is lawfully marketed in the United States. If there is no IND and an exemption is being sought, review the following categories and complete the category that applies (*and delete the inapplicable categories*):

Exempt Category 1

The clinical investigation of a drug product that is lawfully marketed in the United States can be exempt from IND regulations if all of the following are yes:

- i. The intention of the investigation is NOT to report to the FDA as a well-controlled study in support of a new indication for use or to be used to support any other significant change in the labeling for the drug. Yes No

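### The question is how changes in glucose relate to hunger and intake, but item 12 gives power only for contrasts of means and leaves open whether the relation is within or across people

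*Combined protocol and SAP*

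**What the plan says.** **Question.** Section V, item 2 (Background) starts from the glucostatic theory, in which "falling glucose levels exert the opposite effect to stimulate hunger and subsequent food consumption". It states the purpose as "we want to investigate if changes in circulating glucose levels can interfere with eating behavior and food intake". It then reports an eight-person pilot whose findings run from one meal to the next, and concludes that "glycemic excursions following a meal may play a role in hunger and food choices for the subsequent meal".

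**Aim.** Item 1 asks whether "daily glucose profiles as assessed by continuous glucose monitoring for 1 week of normal weight, obese, and diabetic individuals relate to hunger levels"; the same is asked of intake. It does not say whether that relation is within a person over the week or across people.

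**Data.** Item 3 has participants wear the sensor for up to 7 days, keep a food record, and rate hunger before and fullness after eating. There are four groups of 15: lean controls, obese without diabetes, type 2 diabetes matched to the obese group, and type 1 diabetes matched to the controls. Matching is on age and BMI. Of the diabetic participants, item 2 says: "We also plan to study patients with diabetes, who have chronic high glucose levels".

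**Statistics.** Item 12 is the whole of the statistical text. It says "We estimate that a sample size of 15 subjects per group will provide 80% power to detect within group differences of 1.1 standard deviations". On the ratings of liking, wanting and hunger it adds that "we will have at least 80% power to detect between group differences across all glycemic conditions (i.e. main effect of group"). The sizes given are 1.0 SD for that main effect and 1.25 SD within each condition. It names no model, glucose variable, unit of analysis, participant term or group adjustment.

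**The concern.** The background describes something that happens inside a person: glucose rises or falls, and hunger and the next meal follow. The design collects the data to study it, because each participant supplies many rated meals alongside a glucose trace. Item 12 then gives power for quantities that contain no glucose value. It refers to glycemic conditions, which belong to an experiment with set glucose levels. Item 3 describes no such conditions.

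If item 12 alone is followed, the aim goes unanswered. If an analyst fills the gap, two simple choices mislead. One is to correlate weekly mean glucose with weekly mean hunger over all 60 people. The other is to pool all meals as if independent. Thirty of the 60 participants have diabetes and chronically higher glucose, and they may also differ in disease, treatment, diet education or use of a rating scale. Matching on age and BMI does not remove these differences, so either analysis can report them as a glucose effect.

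**Working it through.** **1. What item 12's figures are.** Alpha and sidedness are not stated; two-sided 5% is assumed unless noted. With n = 15 per group:

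- 1.1 SD within group: a paired t-test with zero correlation has standardised difference 1.1/√2 = 0.778 and power 0.800.
- 1.0 SD between groups: the normal two-sample formula gives power 0.782 (exact t 0.753).
- 1.25 SD within a condition: a two-sample t-test at alpha 0.05/3 gives power 0.803 (0.91 at alpha 0.05).

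The figures are recovered, approximately for 1.0 SD, under three different sets of unstated assumptions. All are contrasts of means. None is power for a glucose-hunger slope, and none changes with the number of meals.

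**2. Cost of the naive choices.** The documents give none of the following values; they are assumptions.

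- Four groups of 15, with 21 meals each.
- Person-mean glucose 100/105/150/160 mg/dL, between-person SD 6/8/25/25, within-person SD 12/15/35/50.
- Hunger: person SD 1.2 points, meal residual SD 2.0.
- No glucose effect at all. The diabetic groups rate hunger higher by a fixed offset for other reasons.

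The SD of a person's mean hunger is √(1.2² + 2.0²/21) = 1.28 points, so offsets of 0.3, 0.6 and 1.2 are about 0.2, 0.5 and 0.9 SD. False-positive rates at nominal 5%:

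| Offset (points) | Person means, no group term | Meals pooled as independent | Within-person slope |
|---|---|---|---|
| 0 | 5% | 31% | about 5% |
| 0.3 | 11% | 43% | about 5% |
| 0.6 | 31% | 67% | about 5% |
| 1.2 | 79% | 96% | about 5% |

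Pooling fails even with no offset, because meals from one person share that person's hunger level.

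A second set of assumptions (diabetic groups 2 within-person glucose SDs higher, hunger person SD 1 and residual SD 1) gives the same pattern. At offsets of 0.5 and 1.0 SD, person means reject in about 38% and 89%, pooled meals in 82% and 99%, and person-centred slopes in 4% and 5%.

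**3. Adding group.** With the first set of inputs and group as a factor, the person-level test returns to about 5% at every offset. It still asks a different question. With a true effect of -0.3 points per within-person SD, acting only through deviations from the person's own mean, it rejected in about 5% of runs; the slope test rejected in over 99%.

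**4. What the meal data can detect.** Let residual hunger SD and within-person glucose SD both be 1, M the meals per person and τ the SD of true slopes. The slope detectable with 80% power is d × √(τ² + 1/(M − 3)), with d = 0.778 for 15 people and 0.368 for 60. Two to three meals a day (assumed) over 7 days gives M = 14 to 21.

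- One group of 15: from 0.778 × √(1/18) = 0.18 (M = 21, τ = 0) to 0.778 × √(0.09 + 1/11) = 0.33 (M = 14, τ = 0.3).
- All 60: 0.09 to 0.16 over the same range.
- Difference in slope between two groups of 15 (two-sample d = 1.06): 1.06 × √(1/18) = 0.25 to 1.06 × √(0.09 + 1/11) = 0.45.

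An across-person correlation needs about 0.67 (n = 15) or 0.36 (n = 60) for the same power.

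**The case against.** The strongest reply is that this is an omission in a self-described pilot, and that the plan states no faulty analysis. Much of that stands.

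- **The aim is open.** A reader might infer that item 1 commits to comparing people. It does not. Daily profiles recorded with meal-by-meal ratings fit a within-person reading at least as well, and the pilot findings in item 2 point that way.
- **Item 12 is not purely between-group.** Its first clause concerns a within-group difference and reproduces as a paired contrast. Even so, it ties no glucose value to any meal.
- **The failing analyses are not planned.** Nothing in the protocol proposes correlating person means over all 60 or pooling meals. Item 12 treats group as a factor, and group adjustment removes the group-level bias. The percentages above therefore show what the silence permits.
- **Groups are defined by BMI and diabetes status.** It is tempting to say they were enrolled to differ in glucose, but the lean and obese groups are not selected on it. The argument needs only the diabetic half.

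Two stronger numerical claims also fail.

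- **That a person-level comparison in any group of 15 has almost no power.** Item 2's clamp result implies (5.7 − 4.5)/(90 − 65) = 0.048 points per mg/dL. With between-person glucose SD 6 (lean), r = 0.288/√(0.288² + 1.28²) = 0.22 and power is about 12%. With SD 25 (either diabetic group), r = 1.2/√(1.2² + 1.28²) = 0.68 and power is about 83% (65-82% if slopes vary between people). The clamp slope is also a doubtful guide to free-living glucose. It comes from one induced fall, while the pilot linked hunger more to glucose highs before meals than to lows.
- **That the sign would reverse.** With an effect of -0.3 acting only through deviations from a person's own mean, the person-level correlation is about +0.17 and +0.33 at offsets 0.6 and 1.2. If the same effect acts on absolute glucose (per 28 mg/dL, the average within-person SD), it is -0.09 and +0.09. The reversal depends on an assumption the documents cannot settle.

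**Conclusion.** The point holds as a mismatch between question and statistics. The question and the data are at meal level and within person. The only stated statistical quantities are contrasts of means that contain no glucose value, and one set refers to conditions that the design does not define. This goes beyond missing detail, because following item 12 as it stands leaves the aim unanswered.

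The inflated error rates in the table are conditional. They need an analysis without group adjustment or without a participant term, and, for person means, a hunger difference in the diabetic groups from another cause. They also depend on the assumed glucose gap and variances. Two different sets of assumptions agree on the ordering: the within-person slope holds its nominal error rate and the two naive choices can exceed it widely. The documents do not show that the investigators intend either naive choice.

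This should be changed before analysis. It does not threaten the data collection.

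**What to change.** In items 1 and 12, state that the aim is answered by the within-person association, and name the model.

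- **Outcome:** pre-meal hunger, with meal intake as a second outcome, one record per meal.
- **Exposure:** pre-meal glucose or glucose change (choose and define one), as the deviation from the participant's own mean.
- **Other terms:** person-mean glucose, group, and group × deviation, with a random intercept and random slope per participant.
- **Report:** the within-person slope for each group and the differences between groups. Label the person-mean coefficient as descriptive.
- **Power:** replace the statement about glycemic conditions with the detectable within-person slope, giving the assumed meals per person, residual SD, slope SD and alpha.

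A simpler equivalent is one slope per participant, a one-sample test of the 15 slopes in each group, and a comparison of slopes between groups.

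The cost is wording and analysis on data the protocol already collects, with no added participants, visits or measurements. Two limits should be stated. The slope remains observational: time since the last meal, the content of that meal, activity and treatment timing can all affect it. It also does not address chronic glucose level, which stays in the descriptive person-mean term.
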